Title:	Clinical evaluation of Class I and II cavities restored with the combination of a new flowable and a new sculptable universal bulk-fill composite: A prospective single arm study
Short title / Investigation ID:	Clinical evaluation of a new flowable and a new sculptable universal bulk-fill composite for direct restorative treatment OTCS 36392568
Clinical Investigation Plan, version and date:	Version 3.0, 10.04.2024
Registration:	Registry at ClinicalTrials.gov of the U.S. National Library of Medicine (http://www.clinicaltrials.gov) The trial gets registered in the supplementary federal database (Portal for clinical trials in Switzerland – SNCTP, https://www.kofam.ch/en/snctp-portal/) upon its submission on BASEC. As soon as the new electronic system EUDAMED2 is operational, the clinical investigation will be retrospectively registered, if required.
Category and its rationale:	Category C2 (Art. 6 ClinO-MD) The medical device has no conformity marking.
Name of the MD, Unique Device Identification (UDI), name of the manufacturer	TM Flow UDI not available Shades: A2 plus (LOT: YM0209), A3 plus (LOT: YM0210), A3.5 plus (LOT: YM0211), Bleach plus (LOT: YM0212) TM Fill UDI not available Shades: A2 plus (LOT: YM0205), A3 plus (LOT: YM0206), A3.5 plus (LOT: YM0207), Bleach plus (LOT: YM0208) Manufacturer Ivoclar Vivadent AG [name] SRN-number: LI-MF-000000522 Accessories: Cannulas Luer-Lock
Stage of development:	Pivotal stage The clinical investigation is conducted for a conformity assessment purpose.

Background and rationale:	
Direct restorations in the oral cavity are placed when tooth tissue is partially lost due to caries, trauma, or tooth wear in order to restore the morphology, aesthetics and function of the teeth. Nowadays resin composites used with adhesive systems that bond the restorative material to the tooth structure are most often the materials of choice.
 
Resin composites can be classified by their viscosity in sculptable composites, and flowable composites that show a low viscosity. Resin composites are cured with a polymerization lamp which limits the thickness of material layers to 1-2 mm. Bulk-fill resin composites have been developed to facilitate clinicians' work, reduce working time and simplify the restorative procedure. They can be placed in increments of up to 4-5 mm.
 
If a sculptable (bulk-fill) composite is used in combination with a flowable bulk-fill composite, a first layer of flowable composite can be applied in the cavity and light cured. The flowable composite has the advantage of an easy and fast application, so that the first 4 mm of the cavity are rapidly filled. Afterwards, a capping layer with a sculptable bulk-fill composite is applied and light cured.
 
The newly developed bulk-fill composites TM Flow (flowable) and TM Fill (sculptable) can be light-cured in 3, 5 and 10 seconds (light intensity 3000, 2000 and 1200 mW/cm², respectively). The photons of the curing light activate the initiator for the polymerization reaction, but also create heat which could cause a pulp damage. Damage related to heat stress could lead to postoperative hypersensitivity with elevated pain to cold, heat or chewing.
 
Class I and II cavities need to be filled most often in the daily practice since occlusal and approximal surfaces of molars and premolars are predominantly affected by caries. Class I and II restorations are in areas with the highest occlusal load, so that the material used for these types of restorations is challenged heavily by mechanical forces. New resin composites TM Fill and TM Flow will be used for direct restorations of class I and II cavities (3 seconds light-curing mode) in premolars and molars in this clinical investigation to prove their clinical performance and safety.

Objective(s):	
The overall objective of this clinical investigation is to evaluate the clinical safety and performance of the new resin composites TM Flow and TM Fill.
 
The primary objective is to assess the rate of postoperative hypersensitivity after treatment of class I or II restorations with TM Flow in combination with TM Fill (3 seconds light-curing mode, 3000 mW/cm²).
 
The secondary objective of this study is to assess the long-term clinical efficacy of the materials under investigation in terms of marginal quality retention/fracture rate of the restorations and vitality. The color match, surface lustre and texture, contour and form, occlusion and wear are also assessed. These outcomes provide information about the clinical performance of the material including the aesthetic performance.

Outcome(s):	
The primary outcome of this clinical investigation is the rate of postoperative hypersensitivity (acceptance criterium < 10%).
 
The secondary outcomes focus on tooth vitality and clinical performance of the composites by evaluation of functional (e.g. fracture of the material and retention), biological (e.g. caries at restoration margins) and aesthetic (e.g. color match) properties of the restorations.
 
The primary and the secondary outcomes are assessed using the FDI criteria (Hickel et al., 2022).

Design:	Prospective, single-arm study

Inclusion / exclusion criteria:	
Inclusion criteria:
 
 • Informed Consent signed by the subject • Age: 18-65 years • Indication Class I or II direct restorations in premolars or molars (Replacement of insufficient fillings due to secondary caries, fractures, insufficient marginal adaptation, loss of filling or primary caries) • Cavity width must be at least half of the cusp tip distance • Vital teeth, regular sensitivity • Sufficient language skills • No active periodontitis • Preoperative VAS values < 3 regarding tooth sensitivity and biting 
Exclusion criteria:
 
 • Sufficient isolation of the cavity not possible • Not completed hygiene phase or poor oral hygiene • Missing antagonist, non-occlusion • Missing tooth adjacent to the tooth to be treated • Restorations replacing more than 1 cusp • Caries profunda or very deep cavity • Patients with a proven allergy to ingredients of the used materials (methacrylates) or local anesthetics (Articain, sulfite) • Patients with severe systemic diseases • Pregnancy • Part of the development project team of TM Flow or TM Fill • Staff of the study management team • Staff of the internal clinic
Measurements and procedures:	
Each participant receives one filling in one tooth. The fillings are assessed according to selected FDI criteria at baseline (7-10 days after filling placement) and after 1, 6, 12, 24, 36 and 60 months. At the 1 and 6 month recall the sensitivity is recorded using a visual analogue scale and at all the other recalls the sensitivity is only recorded if necessary. The results are documented by intraoral images.

Intervention:	
The newly developed resin composites TM Flow and TM Fill will be used for the restoration of class I and II cavities (3 seconds light-curing mode, 3000 mW/cm²). The treatment workflow is very similar to other resin composites, for instance the predecessor products Tetric PowerFill and Tetric PowerFlow.

Control intervention (if applicable):	
Not applicable

Number of subjects with rationale:	
61 subjects were calculated for the single-arm study design. Considering a drop-out rate of 5%, 65 subjects will be included in this clinical investigation.

Duration of the investigation:	
60 months for each patient (recruiting phase 4 months)

Investigation schedule:	
May 2024 First-subject-In April 2030 Last-subject-Out

Investigator(s):	
 - [name], [name] - [name], [name] - [name], [name] - [name], [name] - [name], [name] - [name], [name] - [name], [name]
Investigational Site(s):	
This is a single center study.
 
R&D Clinic
 
Ivoclar Vivadent AG
 
[name]
 
[name]
 
Liechtenstein

Statistical considerations:	
The sample size was calculated for a single-arm study design with a one-sided hypothesis (target alpha 5%; power of at least 80%).
 
A one-sided binomial exact test is used to calculate if the probability of postoperative hypersensitivities is lower than 10% (acceptance criterium).

Compliance statement:	
This investigation will be conducted in compliance with the CIP, the current version of the Declaration of Helsinki, ISO14155, ICH-GCP (as far as applicable) as well as all national legal and regulatory requirements.

ABBREVIATIONS

AE	Adverse Event
ADE	Adverse Device Effect
ASADE	Anticipated Serious Adverse Device Effect
ASR	Annual Safety Report
CA	Competent Authority (Amt für Gesundheit Liechtenstein)
CEC	Competent Ethics Committee
CIP	Clinical investigation plan
ClinO	Ordinance on Clinical Trials in Human Research (in German KlinV, in French Oclin, in Italian OSRUM)
ClinO-MD	Ordinance on Clinical Trials with Medical Devices (in German: KlinV-Mep, in French: Oclin-Dim, in Italian: OSRUM-Dmed)
CRF	Case Report Form (pCRF paper CRF; eCRF electronic CRF)
DD	Device Deficiency
DMC / DSMC	Data Monitoring Committee, Data Safety Monitoring Committee
FDI	Fédération Dentaire Internationale
Ho	Null hypothesis
H1	Alternative hypothesis
HRA	Federal Act on Research involving Human Beings (in German: HFG, in French: LRH, in Italian: LRUM)
IB	Investigator's Brochure
ICF	Informed Consent Form
ICH-GCP	International Council for Harmonisation – guidelines of Good Clinical Practice
IFU	Instruction For Use
ISF	Investigator Site File
ISO	International Organisation for Standardisation
ITT	Intention to treat
MedDO	Medical Devices Ordinance (in German: MepV, in French: Odim, in Italian: Odmed)
MD	Medical Device
MDR	Medical Device Regulation (EU) 2017/745 of 5 April 2017
PI	Principal Investigator
SADE	Serious Adverse Device Effect
SAE	Serious Adverse Event
SDV	Source Data Verification
SNCTP	Swiss National Clinical Trials Portal
SOP	Standard Operating Procedure
USADE	Unanticipated Serious Adverse Device Effect
VAS	Visual Analogue Scale

INVESTIGATION SCHEDULE

Study Periods	Screening	Treatment, Intervention Period	Follow-up							
Visit	0	1	2	3	4	5	6	7	8	
Time (hour, day, week)	-3- (-30) d	0 d	7-10 d	1 m	6 m	12 m	24 m	36 m	60 m	
Patient Information and Informed Consent	x									
Medical History	x									
In- /Exclusion Criteria	x									
Tooth Examination	x									
Pregnancy Test	x									
Vitality test	x	x	x	x	x	x	x	x	x	
VAS for tooth sensitivity		x	x	x	x	x*	x*	x*	x*	
Preparation of tooth		x								
Placement of restoration		x								
Primary Variables			x	x	x	x	x	x	x	
Secondary Variables			x	x**	x	x	x	x	x	
Photographs	x	x	x	x	x	x	x	x	x	
Adverse events and device deficiencies		x	x	x	x	x	x	x	x	

* Assessment will only be done if there is a patient complaint for paraesthesia or pain

** Not all variables will be assessed (only fracture of material, surface luster, color match)

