The modern curing lights use LED technology whose photons activate the initiators within the resin composite. Lamps with different power density are available. They vary between 700 mW/cm² and 5,700 mW/cm² (Christensen et al., 2019). The higher the power density the shorter the polymerization time. The polymerization time required for a lamp with 1.200 mw/cm² is 10 seconds, with 2,000 mw/cm² it is 5 seconds and with 3,000 mW/cm² it is 3 seconds. However, each increment must be cured separately which results in multiple curing shots. The photons of the curing light activate the initiator, but also create heat which has raised the concern that heat might be transmitted from the cavity to the pulp with the potential risk of pulp damage. In addition, the exothermal polymerization reaction of dental composites is delivering also heat to the tooth contributing to the increase of the pulpal temperature. The flowable

composites show a higher exothermal polymerization reaction than sculptable composites due to the higher monomer content. Possible damage related to heat stress comprises (1) reversible pulpitis with elevated pain to cold, heat or chewing after the treatment (post-operative hypersensitivity), (2) irreversible pulpitis with or without pain which makes a root canal treatment necessary or (3) internal resorption in the pulp chamber.

Post-operative hypersensitivity is reversible in most cases and lasts from one week to several months (Major et al., 2002). Besides heat stress generated by the curing lamp and by the exothermic reaction of the resin composite, many other factors may influence the occurrence of sensitivity such as the remaining dentin thickness that separates the cavity from the pulp chamber, the size of the cavity and previous damage of the tooth.

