6.4.1 Datasets to be analysed, analysis populations

The data collected of all eligible participants will be used for the statistical data analysis.

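### The eligibility check is scheduled before the preoperative VAS is recorded, and the primary analysis set rests on an undefined term, "eligible", so a treated tooth could be left out late

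*Combined protocol and SAP*

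**What the plan says.** - **Timing of the eligibility check.** In the Investigation Schedule the row "In- /Exclusion Criteria" has one mark, at Visit 0 (day -3 to -30).
- **Timing of the VAS.** The row reads "VAS for tooth sensitivity x x x x x* x* x* x". That is eight marks for nine visits, and the last four carry the complaint-only footnote. Section 3.1 makes the VAS complaint-only from the 1-year recall, so those four are Visits 5 to 8 and the unmarked visit is Visit 0.
- **Criteria concerned.** The synopsis requires "Preoperative VAS values < 3 regarding tooth sensitivity and biting" for inclusion and lists "Caries profunda or very deep cavity" as an exclusion, with no depth threshold and no time of assessment.
- **Other rows.** "Tooth Examination" is marked at screening only, and its content is not described. "Preparation of tooth" is marked at Visit 1, the same visit as placement.
- **Analysis set.** Section 6.4.1: "The data collected of all eligible participants will be used for the statistical data analysis". The term is not defined. ITT appears in the abbreviation list and nowhere else.
- **Link to the outcome.** Section 1.1 names "the remaining dentin thickness that separates the cavity from the pulp chamber, the size of the cavity and previous damage of the tooth" among the influences on sensitivity, section 6.1 names cavity depth and size again, and section 3.1 reads postoperative VAS against the preoperative values.

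**The concern.** Two gaps meet here. First, the schedule asks for an eligibility decision before one of the required values is collected, and it marks no confirmation on the day the value arrives. Second, the primary analysis set depends on eligibility and not on treatment, with no rule for a tooth that was restored and later found to breach a criterion.

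The criteria involved bear on the primary outcome, so a tooth in breach may well be more likely than others to count as an event. Little else in the plan limits discretion. The study is single-arm in the sponsor's own clinic, section 4.2.3 lists no further bias control, data are examined after each recall (section 6.4.4), and the principal investigator does the analysis (section 6.4.2). If membership of the set is settled once grades are visible, the hypersensitivity rate can move towards passing the 10% limit. The limit is only a few events wide, so small changes in the set matter.

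**Working it through.** **Inputs (sections 6.1 and 6.2).** One-sided exact binomial test, P0 = 0.10, P1 = 0.024, alpha 0.05, n = 61, stated power 0.82, drop-out 5%, 65 enrolled.

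**Formula.** For x events in n teeth, p = P(X ≤ x | n, 0.10) = Σ C(n,k)·0.1^k·0.9^(n−k), summed over k = 0 to x. The limit c is the largest x with p ≤ 0.05. Power is P(X ≤ c | n, 0.024).

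**The plan's own figure.** At n = 61, c = 2, the attained alpha is 0.0491 and power is 0.8195. This reproduces the stated 0.82. 61/0.95 = 64.2, rounded up to 65. The sample size calculation is not in question.

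**Effect of removing one event.** The limit is 2 events at every n from 61 to 65, and 1 event at n = 60.

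| All treated teeth | p | After removing one event | p | Reversed? |
|---|---|---|---|---|
| 3/65 | 0.0996 | 2/64 | 0.0389 | yes |
| 3/64 | 0.1063 | 2/63 | 0.0421 | yes |
| 3/63 | 0.1134 | 2/62 | 0.0455 | yes |
| 3/62 | 0.1210 | 2/61 | 0.0491 | yes |
| 3/61 | 0.1290 | 2/60 | 0.0530 | no |

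**Type I error at n = 65 and a true rate of 10%.**
- No removal possible: P(X ≤ 2) = 0.0011 + 0.0077 + 0.0273 = 0.036.
- One event removable: the test passes whenever X ≤ 3, so the error is at most 0.036 + 0.0636 = 0.0996.

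The second figure is an upper bound. It assumes that whenever exactly three events occur, one of them is in a tooth that can be declared ineligible.

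**A milder case (assumed inputs).** Let a share f of the 65 teeth prove ineligible on day 0, keep the overall event rate at 10%, and drop an ineligible tooth only if it has an event.

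| f | Event risk in ineligible teeth | Type I error |
|---|---|---|
| 5% | 10% (same as overall) | 0.047 |
| 5% | 20% | 0.060 |
| 10% | 10% (same as overall) | 0.060 |
| 10% | 20% | 0.098 |

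The documents give no value for f or for the risk in such teeth. These figures show a range, not an estimate.

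**Removal regardless of outcome.** This can work against the sponsor. If the analysed number falls from 61 to 60, the limit falls from 2 events to 1 and power at 0.024 falls from 0.82 to 0.58.

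**The case against.** The strongest reply has four parts.

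1. **If eligibility is decided only at Visit 0, the eligible set is fixed before treatment, and later removal would need a step the plan does not contain.** This is a fair reading and it would close the second gap. But the plan does not state it, and it would mean that the VAS criterion plays no part in the eligibility decision. Either the set is fixed without the VAS, or the VAS is applied later at an unstated time.

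2. **The Visit 1 VAS is taken before exposure.** The criterion is worded as preoperative, and the VAS row stands above preparation and placement. This stands: the value exists in time to be used. What is missing is a scheduled point at which it is used and recorded. A reader might infer that the plan intends to restore ineligible teeth; the documents do not say so.

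3. **Depth may be judged at screening.** A tooth examination, vitality test and photographs are marked there, and deep caries can be a diagnosis made before preparation. This also stands. A reader might infer that depth is known only on treatment day, but the documents do not establish that. It is reasonable to expect that final depth follows preparation, and no more than that.

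4. **Harm needs selective removal of events, which is presumed.** Correct. Dropping teeth whatever their outcome tends to cost power. The bias is a possibility left open by the wording, not a stated intention.

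**Conclusion.** The point holds in a limited form. The mismatch between the schedule and the VAS criterion can be read directly from the documents and needs no assumption. The lack of a definition, a decision time and a decision maker for eligibility in section 6.4.1 is equally plain.

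The consequence for the primary test is conditional. If one treated tooth with an event could be ruled ineligible after its grade is known, a failing result could become a passing one with 62 to 65 analysed, and type I error at n = 65 could rise from 0.036 to at most 0.0996. It does not follow that one tooth decides the result at every planned number: at n = 61, the number the power calculation uses, 2/60 still fails. Nor does the text support a claim that late exclusion is planned. It supports only that late exclusion is not ruled out. The sample size and the test itself are sound on this point.

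**What to change.** 1. **Reconcile the schedule with the synopsis criteria.** The visit at which eligibility is confirmed and recorded should be one where the preoperative VAS and the information for the cavity criteria are available, and it should precede placement. How a tooth that does not meet a criterion is managed clinically is for the investigators to state.

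2. **Redefine the set in section 6.4.1.** Make the primary analysis set all participants in whom TM Flow/TM Fill was placed, with membership fixed at placement and no later exclusion for an eligibility breach. Any set that leaves out breaches is a sensitivity analysis only.

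**Cost.** One more eligibility record at treatment, a change to the schedule and a sentence in 6.4.1. The observed rate may be slightly less favourable if a breach is found after placement. Sample size, endpoint and test do not change. If all 65 are analysed, the limit stays at 2 events, with alpha 0.036 and power 0.795. Power is then marginally under the 80% target, because the exact limit does not move between 61 and 65.

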1. BACKGROUND AND RATIONALE

1.1 Background and Rationale for the clinical investigation

Caries lesions are a chronic disease that is widely spread among the population all over the world affecting 60-90% of children and the vast majority of adults in industrialised countries. (Pitts et al., 2017). Caries in posterior teeth (molars or premolars) occurs mostly in fissures or on approximal surfaces below the contact point of two neighboring teeth. In order to treat the disease caries affected tissue is removed. This leads either to class I cavities which have just one outer surface on the occlusal aspect of a posterior tooth or class II fillings, which are characterized with two outer filling surfaces on the occlusal and approximal aspect.

Over the last three decades, caries prevalence has decreased in all age groups in modern Western countries (Jordan et al., 2019). For example, in European, caries prevalence in adults has declined by about 20% between 1996 and 2016 (Kassebaum et al., 2017). In Germany the cumulative caries experience has decreased from 1.1 billion DMFT (decayed/missing/filled teeth) in 2000 to 867 million in 2015 and is expected to further decrease to 740 million in 2030 (Jordan et al., 2019). However, not all societal groups have benefitted equally from this decline (Jordan et al., 2019). There is evidence for an association between low socio-economic status and a higher risk of having dental caries. In addition, on an international level - associated with population growth and increased tooth retention - the number of people affected by dental caries has grown substantially, increasing the total burden globally by 37% for untreated caries (Kassebaum et al., 2017).

The evolution of carious lesion can be fast (acute) or slow (chronic). Both evolution rates are leading to loss of tooth structure over time and the morphology and function of teeth is affected. The goal of therapeutic procedures is to restore the morphology, aesthetics, and function of teeth by replacing the missing tooth substance with restorative materials. The therapeutic procedures are of two types: direct restorative procedures, where the tooth structure is restored directly in the oral cavity and indirect procedures where the restorations are manufactured either in the dental laboratory or chairside in a digital workflow.

Direct (in the oral cavity of the patient) dental restorations are placed when sound tooth tissue (enamel and/or dentin) is partially lost due to caries, trauma, or tooth wear. When carious lesions no longer can be remineralized or arrested with non-invasive methods such as fluoride applications, the defect needs to be restored. For the direct restorative procedures dental resin composites and amalgam are mostly used in the daily practice. Resin composites are tooth-colored materials. Resin composites are used with adhesive systems that bond the restorative material to the tooth structure. This allows dentists to accomplish defect-oriented preparations, limiting the removal of tooth substance to the area of the defect that needs to be restored. Composite resins are delivered in various shades, opacities and translucencies which allows aesthetically pleasing restoration of the original tooth structure.

Resin composites can be classified by their viscosity in sculptable composites, showing a high viscosity respectively flowable composites showing a low viscosity. Resin composites are cured with a polymerization lamp which limits the thickness of material layers to 1-2 mm. Therefore, resin composites must be placed in incremental layers. Bulk-fill resin composites have been developed to facilitate clinicians' work, reduce working time and simplify the restorative procedure (Kruly et al., 2018). They can be placed in increments of up to 4-5 mm as they either contain special light initiators which polymerize the resin in thicker increments or as the material is more translucent which allows the light to penetrate into deeper areas of the resin.

The sculptable (bulk fill) composites can be used either alone or in combination with flowable bulk-fill composites. If such a combination is used to restore cavities a first layer of up to 4 mm thickness of flowable composite is applied in the cavity and light cured. The flowable composite has the advantage of an easy and fast application, so that the first 4 mm of the cavity are rapidly filled. Afterwards a capping layer of sculptable bulk-fill composite is applied, modelled and light cured. In this manner the cavities are restored even more rapidly.

The modern curing lights use LED technology whose photons activate the initiators within the resin composite. Lamps with different power density are available. They vary between 700 mW/cm² and 5,700 mW/cm² (Christensen et al., 2019). The higher the power density the shorter the polymerization time. The polymerization time required for a lamp with 1.200 mw/cm² is 10 seconds, with 2,000 mw/cm² it is 5 seconds and with 3,000 mW/cm² it is 3 seconds. However, each increment must be cured separately which results in multiple curing shots. The photons of the curing light activate the initiator, but also create heat which has raised the concern that heat might be transmitted from the cavity to the pulp with the potential risk of pulp damage. In addition, the exothermal polymerization reaction of dental composites is delivering also heat to the tooth contributing to the increase of the pulpal temperature. The flowable

composites show a higher exothermal polymerization reaction than sculptable composites due to the higher monomer content. Possible damage related to heat stress comprises (1) reversible pulpitis with elevated pain to cold, heat or chewing after the treatment (post-operative hypersensitivity), (2) irreversible pulpitis with or without pain which makes a root canal treatment necessary or (3) internal resorption in the pulp chamber.

Post-operative hypersensitivity is reversible in most cases and lasts from one week to several months (Major et al., 2002). Besides heat stress generated by the curing lamp and by the exothermic reaction of the resin composite, many other factors may influence the occurrence of sensitivity such as the remaining dentin thickness that separates the cavity from the pulp chamber, the size of the cavity and previous damage of the tooth.

In an attempt to clarify the relationship between radiant exposure values and pulp temperature, Arrais et al. (2019) evaluated the in-vivo pulp temperature rise in premolars with cervical cavities which were exposed to 10 seconds of 2,000 mW/cm² or 2x3 seconds of 3,000 mW/cm² (Arrais et al., 2019). The teeth were extracted 2 hours after light exposure and histologically and immunochemically examined for signs of early inflammatory indicators like IL- β and TNF- α . The results showed a similar histological and immunochemical expression in both groups. A prospective clinical study on 62 posterior resin composite bulk-fill restorations that had been cured with a 3,000 mW/cm² curing lamp for 3 seconds found that after 12 months, none of the treated teeth had suffered loss of sensitivity (vitality). However, in two independent clinical trials the rate of post-operative hypersensitivity at baseline was slightly higher compared to restorations that had been cured with the conventional technique. Most cases of post-operative sensitivity subsided without intervention within several weeks. There were a few restorations that had manageable remnant post-operative sensitivity for which the subjects did not want intervention (Lawson et al., 2020, 2022, Enggist, 2018).

TM Fill (sculptable) and TM Flow (flowable) are dental bulk-fill composites that can be applied in up to 4 mm layers and can be light cured in 10, 5 or 3 seconds. The products are not bearing a CE mark and are not yet available on the market, so no clinical studies are available with these two products regarding the incidence rate of postoperative hypersensitivity and clinical performance of the product. The aim of this study is to assess the incidence rate of postoperative hypersensitivity, when class I and II cavities are directly restored with TM Fill in combination with TM Flow, both being light cured in the 3 seconds curing mode (3,000 mW/cm²). The application of a first layer of up to 4 mm TM Flow is considered the worst-case scenario, due to the higher exotherm polymerization reaction of flowable composites. By this clinical study not only the pulp response of the teeth to the materials in combination with the 3 seconds-curing mode is determined, but also the clinical performance of the material by the assessment of the secondary outcomes like tooth vitality, marginal quality, fracture of material and retention loss, surface quality and aesthetics.

